### 5.2.2. Risk sets

The risk set for each study dose cohort will include adults  $\geq 18$  years with or without comorbidities associated with increased risk of progression to severe COVID-19 who do not discontinue or receive another COVID-19 vaccination or have a SARS-CoV-2 infection (positive PCR result or positive serology test) prior to the start of the observation period (ie before their follow-up is counted under the relevant dose cohort). Subjects where the date of unblinding is unknown will also be excluded from the risk sets since it is not possible to accurately determine the start of the open-label observational period.

Additionally, for the one-dose cohort, subjects that are unblinded and receive a second Ad26.COV2.S vaccination on the same day as unblinding will be excluded from the risk set, since they are not considered to contribute one whole day of follow-up.

An overview of the risk sets and the in and exclusion criteria are presented in [Table 5](#).

### 5.2.3. Observational period

The start of the observational period differs per dose cohort as follows: for subjects in the one-dose schedule cohort the observation period starts at the date of unblinding. If the date of the first Ad26.COV2.S vaccination is after the date of unblinding, then the observational period starts at the date of first Ad26.COV2.S vaccination. For subjects in the two-dose schedule cohort and subjects in the booster dose schedule cohort the observation period starts at the date of the second dose. If the date of the second dose is prior to unblinding then the observational period will start from the date of unblinding. Note that the first 28 days after vaccination, named the blackout period, are excluded. The start of the observational period is presented by dose cohort in [Table 5](#).

The end of the observational period is also different per dose cohort. The observational period ends when the participants experience an endpoint of interest, or the observational period is censored when an outside vaccination is received, 30 days prior to the site approval of PA7 or when the participant discontinued. Additionally for the one-dose cohort the observational period is censored when a second Ad26.COV2.S vaccination is received, and for the two-dose cohort and the booster dose cohort the observational period is censored when a third Ad26.COV2.S vaccination is received.

The calculation of follow-up time is described in section [5.2.5](#).

### 5.2.4. Efficacy endpoints

Details on the COVID-19 case classification are described in the SAP for the double-blind phase. As described in that SAP, COVID-19 classifications are performed by two methods: one consisting of a programmed algorithm and one consisting of an assessment by the CSAC. Of note, as described in the introduction, the clinical development program has moved from “Development” to a “Life cycle management” phase. Hence the scope and the extent of the open-label analysis have been reduced. No efficacy analysis will be assessed during the open-label phase of the trial. No relative vaccine efficacy nor group comparisons will be calculated. The efficacy endpoints will be presented descriptively per dose cohort. Note that since July 8 2022, no suspected COVID-19 cases were sent for adjudication. Additionally some suspected COVID-19 cases that were sent prior to July 8 2022 were never adjudicated. Therefore, in the open-label phase, not all COVID-19 cases will have an evaluation of severity by the CSAC. Therefore all tables, figures and listings presenting the COVID-19 cases that occurred during the open-label phase are assessed by the programmed algorithm only.

For each of the endpoints listed below, the number of cases and incidence per 100 person-years will be presented for each study dose cohort by month. Cumulative incidence plots per endpoint by calendar time for each study dose cohort will be provided. For the endpoint of moderate to severe/critical COVID-19 this plot will be repeated by region and by country.

1. Molecularly confirmed moderate to severe/critical COVID-19 infection at least 28 days after last vaccination

2. Molecularly confirmed severe/critical COVID-19 infection at least 28 days after last vaccination
3. Molecularly confirmed symptomatic COVID-19 infection at least 28 days after last vaccination
4. Molecularly confirmed COVID-19 infection requiring medical intervention at least 28 days after last vaccination
5. COVID-19 related death at least 28 days after last vaccination

#### **5.2.4.1. Programmed algorithm for molecularly confirmed COVID-19 infection requiring medical intervention**

A COVID-19 infection is considered to require medical intervention if the subject has one of the following recorded as a medical encounter in the CRF for a molecularly confirmed COVID-19 episode:

- "HOSPITAL INPATIENT DEPARTMENT"
- "MECHANICAL VENTILATION USE"
- "INTENSIVE CARE UNIT"

#### **5.2.4.2. Programmed algorithm for COVID-19 related death**

A COVID-19 infection is considered to be a COVID-19 related death if the participant had a fatal AE related to COVID-19 with a molecularly confirmed PCR test.

#### **5.2.5. Follow-up for Efficacy Endpoints**

Median, minimum, maximum, and interquartile range of the follow-up time in the observational period will be provided by study dose cohort of the efficacy risk set. The reason for the end of follow-up will also be included in the table.

For subjects in the one-dose schedule cohort the follow-up time is calculated from date of unblinding. If the date of the first dose is after the date of unblinding, then the follow-up time will start at the date of first dose. For subjects in the two-dose schedule cohort and subjects in the booster dose schedule cohort the follow-up time starts from the date of the second dose. If the date of the second dose is prior to unblinding then the follow-up time will start from the date of unblinding. The first 28 days after vaccination are excluded. Additionally follow-up time from first study vaccination and follow-up time from last Ad26.COV2.S vaccination will also be presented by study dose cohort of the efficacy risk set.

The follow-up time for an individual will be censored at i) the date of receipt of another authorized/approved COVID-19 vaccine, including the Janssen COVID-19 vaccine if received outside of the study, ii) the date of study discontinuation or completion, iii) 30 days prior to the date of study site approval for PA7, or iv) the date the endpoint was observed, whichever occurred first. Additionally, for subjects in the single-dose schedule cohort the date of a second

Ad26.COV2.S vaccination will be considered as a reason for censoring and for subjects in the two-dose and the booster dose cohorts, the date of a third Ad26.COV2.S vaccination will be considered as a reason for censoring.

Kaplan-Meier (KM) plots will be produced for the follow-up time in the observational period for each study dose cohort in the efficacy risk set for each endpoint overall and by country. KM plots of follow-up time from first study vaccination and for follow-up time from last Ad26.COV2.S vaccination will also be produced for each study dose cohort in the efficacy risk set for each endpoint overall. Additionally, a graph using calendar time will be produced to present the number of subjects at risk for moderate to severe/critical COVID-19 during the observational period in each study dose cohort overall and by country and by region. Also a graph using calendar time for the full set of participants from the FAS, including participants who were not part of the risk set, will be produced to present the number of subjects at risk for moderate to severe/critical COVID-19 from the start of the study by vaccination group.

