## 5.2. Efficacy Analysis of the Open-Label Active Follow-up Phase

Note that no hypothesis testing and no efficacy evaluations will be performed. All endpoints will be evaluated using descriptive statistics. These descriptive summaries can not support any comparisons between groups or any interpretation regarding difference between groups.

The efficacy analyses will be based on a subset of the participants of the FAS, ie the participants who are at risk to develop an endpoint in the open-label active phase. These subsets are called risk sets and depend on the vaccination schedule the participants received as indicated in Table 5 and explained in Sections 5.2.1 and Section 5.2.2.

As only the data under the open-label active follow-up is considered, an observational period is defined for each of the vaccination groups (Table 5 and explained in Section 5.2.3). Only the efficacy data within this observational period will be summarized. Efficacy endpoints for the vaccination groups outside of this observational period, ie within 30 days prior to the PA7 site approval, will be listed.

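### Kaplan-Meier curves timed from first or last vaccination have no delayed-entry rule, so ordinary Kaplan-Meier would count event-free waiting time as time at risk and understate cumulative incidence

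*SAP*

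**What the plan says.** - **Who is in the risk set.** SAP section 5.2.2 and Table 5 admit a participant only if he or she did not discontinue, receive another COVID-19 vaccine, or "have a SARS-CoV-2 infection (positive PCR result or positive serology test) prior to the start of the observation period".
- **When observation starts.** In the one-dose cohort, section 5.2.3 says that "for subjects in the one-dose schedule cohort the observation period starts at the date of unblinding", or at the first Ad26.COV2.S dose if that is later. The two-dose and booster cohorts start at the second dose, but "If the date of the second dose is prior to unblinding then the observational period will start from the date of unblinding". In all cohorts "the first 28 days after vaccination, named the blackout period, are excluded".
- **Which events count.** Section 5.2: "Only the efficacy data within this observational period will be summarized".
- **Which curves are drawn.** Section 5.2.5 has a main Kaplan-Meier plot of follow-up within the observational period. It then adds that "KM plots of follow-up time from first study vaccination and for follow-up time from last Ad26.COV2.S vaccination will also be produced", and these are "for each study dose cohort in the efficacy risk set for each endpoint overall". Section 5.2.4 adds: "Cumulative incidence plots per endpoint by calendar time for each study dose cohort will be provided".

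Section 5.2.5 fixes the start of the main clock and the censoring dates. For the two vaccination-based clocks it gives the time origin but not the time at which a participant joins the number at risk. Delayed entry (left truncation) is not mentioned anywhere in the SAP.

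**The concern.** On the two vaccination-based clocks, the origin can lie well before the start of observation. A risk-set member cannot have an event in between: an infection in that interval removes the person from the set, and events outside the observational period are not summarised. The interval is therefore event-free by construction.

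If the program computes time from vaccination to event or censoring and runs ordinary Kaplan-Meier, these people sit in the denominator throughout the interval. Early incidence then looks close to zero and the curve stays too low afterwards. A reader looking at cases against time since vaccination would see better early protection than the data contain. The size depends on the entry delay, so it also differs between cohorts.

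**Working it through.** **Inputs from the SAP**
- Entry at the later of unblinding and the relevant dose, with the first 28 days after vaccination excluded (5.2.3, Table 5).
- Booster at least 3 months, preferably 6 to 12 months, after the first Ad26.COV2.S dose (1.2). With the 28 days, entry on the first-dose clock is at roughly 4-13 months.
- For crossed-over participants the first study vaccination can be placebo (Table 2), which lengthens the gap.
- There is no stated figure to reproduce: the open-label phase has no hypothesis and no sample size (sections 2 and 3.1).

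**Assumptions, because the SAP gives neither quantity**
- Constant hazard of 5, 10 or 25 per 100 person-years.
- Entry delay d uniform over the ranges shown below.
- One year of follow-up after entry.

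**Hand calculation.** With a low hazard λ, the two estimates at month t are approximately:
- without delayed entry: λ × mean of max(t − d, 0);
- with delayed entry: λ × (t − earliest d).

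λ cancels, so the ratio depends mainly on the delays. At t = 12 months:
- Booster cohort, first vaccination, d from 4 to 13: mean = (8²/2)/9 = 3.56; 3.56/(12 − 4) = 0.44.
- First vaccination, d from 2 to 8: (12 − 5)/(12 − 2) = 0.70.
- Two-dose cohort, last dose, unblinding 0-6 months later, with entry no earlier than 28 days (0.92 months): mean entry = [0.92² + (6² − 0.92²)/2]/6 = 3.07; (12 − 3.07)/(12 − 0.92) = 0.81.

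**Simulation.** 200,000 participants per scenario, with anyone infected before entry excluded. The percentages are cumulative incidence at 10 per 100 person-years; the ratios span all three hazards.

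| Origin and assumed entry | Read at | Ordinary KM | Delayed entry | Ratio |
|---|---|---|---|---|
| Booster cohort, first vaccination, 4-13 months | 1 year | 3.0% | 6.3% | 0.42-0.47 |
| Same | 1.5 years | 7.7% | 10.9% | 0.69-0.72 |
| First vaccination, 2-8 months | 1 year | 5.6% | 7.9% | 0.71-0.73 |
| Two-dose cohort, last dose, unblinding 0-6 months later | 1 year | 7.2% | 8.8% | 0.81-0.82 |
| Booster cohort, last dose, unblinded before booster | 1 year | 8.8% | 8.8% | 1.00 |

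The delayed-entry estimate recovers the simulated value from the earliest entry onward. For the two-dose row the true value after day 28 is 8.8%. For the booster row from first vaccination it is 1 − exp(−0.10 × 8/12) = 6.4%, which is incidence from month 4, not from vaccination.

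**What is not biased.** The rate computed on observational-period time came out at about 10 per 100 person-years for a true 10. A gap of exactly 28 days shared by everyone leaves the curve flat and then correct, hence the ratio of 1.00.

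**The case against.** The strongest reply is that the SAP is silent on delayed entry and does not rule it out. Restricting summaries to the observational period is compatible with entering people when observation starts. That is fair: the fault is a missing rule. But the stated origin and risk set, run through default Kaplan-Meier, give a wrong curve, so the omission is more than a detail of programming.

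A second reply is that everything here is descriptive, and that sections 5.1 and 5.2 rule out group comparisons. This limits the consequence. It does not remove it, because the error lies within each curve.

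A reader might also infer three stronger things that the SAP does not support:
- **That the calendar-time curves share the bias.** Section 5.2.4 names no estimator, and the companion calendar-time graph in 5.2.5 counts people at risk during the observational period, which implies staggered entry. If everyone were counted from a common date, the simulated ratios would be 0.88-0.89, 0.73-0.77 and 0.59-0.61 for entry spread over 3, 6 and 10 months. That is a risk, not something the text establishes.
- **That the duration-of-protection result is distorted.** The estimand table in 1.1 summarises that objective by monthly incidence per 100 person-years, which this mechanism does not bias.
- **That the booster cohort is worst on every clock.** That holds only from first vaccination. Measured from the last dose, participants boosted under Amendment 6 after unblinding, and placebo participants crossed over at or after unblinding, have only the common 28-day gap.

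**Conclusion.** The point stands for two sets of supplementary curves: those from first study vaccination wherever entry is delayed (most in the booster cohort), and those from last dose for participants whose last dose preceded unblinding (the two-dose cohort and part of the one-dose cohort). Without an entry rule, ordinary Kaplan-Meier would report roughly 0.4 to 0.8 of the delayed-entry cumulative incidence at 1 year under the delays assumed here. In the booster scenario the shortfall narrows by 1.5 years. The direction follows from the SAP's own definitions; the size rests on assumed hazards and delays. The conclusion also takes a Kaplan-Meier plot drawn for each endpoint to be a time-to-endpoint curve, which is the natural reading. The main Kaplan-Meier plot and the incidence rates are sound on this point, and no planned inference depends on the affected curves.

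**What to change.** In 5.2.5, state that for Kaplan-Meier plots with origin at first study vaccination or last Ad26.COV2.S vaccination, each participant joins the risk set by left truncation at the start of his or her observational period (the later of unblinding and the relevant dose, after the 28-day exclusion) and leaves at the event or censoring date. Print numbers at risk under that rule, and note that each curve describes incidence from the earliest entry onward. State the same entry rule in 5.2.4 for the calendar-time cumulative incidence plots, so that they agree with the number-at-risk graph.

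The cost is a sentence in each section and an entry-time argument in the program; no new data are needed. The drawback is that the early part of each curve rests on few participants and will be less stable, which the printed numbers at risk will show.

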### **5.2.6. Subgroups**

For each of the endpoints listed in section [5.2.4](#) the number of cases and incidence rates per 100 person-years will be presented by month and the following subgroup:

- Country and/or region

### **5.2.7. Supportive Analysis**

#### Demographics and baseline characteristics

Demographic tables including baseline characteristics comparing the study dose cohort risk sets.

#### *Severity ratio*

The severity ratio will be calculated as the ratio between severe cases and both severe and moderate cases. This ratio will be presented for each of the study dose cohorts.

#### *Long COVID-19 ratio*

The long COVID-19 ratio will be calculated as the ratio between long COVID-19 cases and both long and short cases. This ratio will be presented for each of the study dose cohorts. An episode lasting more than 28 days is considered to be a long COVID-19 case and an episode lasting 28 days or less a short COVID-19 case.

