### **1.1. Objectives, Endpoints**

The list of objectives and endpoints for the open-label active surveillance phase and for the open-label passive follow-up phase can be found in PA7. Note that no efficacy evaluations or group comparisons will be performed. All objectives will be evaluated using descriptive statistics.

As of protocol amendment 2, subjects were allowed to receive vaccination outside of the study while still following the same protocol scheduled procedures as those subjects that remained in the study with the Ad26.COV2.S vaccine. The safety for subjects that received other vaccines outside of the study will also be described. No tabulations of efficacy data following vaccines received outside of the study will be provided.

The exploratory endpoints associated with the correlate of risk/efficacy objective will not be evaluated in this study. Correlate of risk/efficacy objectives will be evaluated in the context of study COV3001.

The exploratory endpoints associated with immunogenicity objectives will not be evaluated in the open-label active surveillance phase.

Estimands for the open-label active surveillance analysis:

Objectives	Endpoints/Variable	Population	Intervention	Intercurrent events	Summary measure
Safety	SAEs, AEIs and AESIs from study start until PA7 site approval	Adults>= 18 years old	Ad26.COV2.S, placebo, one or more doses of mRNA + Ad26.COV2.S OR one or more doses of non-mRNA + Ad26.COV2.S, mixed schedule	LTFU	Number of subjects with events and incidence rates per 100 person years per reporting period
Molecularly confirmed a , symptomatic COVID-19 b	Symptomatic COVID-19 according to mild, moderate or severe programmed algorithmic definition, with onset at least 28 days after last vaccination.	Adults>= 18 years old	Single dose Ad26.COV2.S  Two doses Ad26.COV2.S (maximum of 70 days between doses)  Booster dose Ad26.COV2.S (minimum of 71 days between doses)	LTFU-Outside vaccinations	Number of subjects with events and incidence rates per 100 person-years

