Molecularly confirmed a , severe/critical COVID-19 b	Severe/critical COVID-19 according to programmed algorithmic definition, with onset at least 28 days after last vaccination	Adults>= 18 years old	Single dose Ad26.COV2.S  Two doses Ad26.COV2.S (maximum of 70 days between doses)  Booster dose Ad26.COV2.S (minimum of 71 days between doses)	LTFU- Outside vaccinations	Number of subjects with events and incidence rates per 100 person-years

Objectives	Endpoints/Variable	Population	Intervention	Intercurrent events	Summary measure
Molecularly confirmed a , COVID-19 b cases requiring medical intervention	COVID-19 cases according to programmed algorithmic definition requiring medical intervention, with onset at least 28 days after last vaccination	Adults>= 18 years old	Single dose Ad26.COV2.S  Two doses Ad26.COV2.S (maximum of 70 days between doses)  Booster dose Ad26.COV2.S (minimum of 71 days between doses)	LTFU- Outside vaccinations censoring	Number of subjects with events and incidence rates per 100 person-years
COVID-19 related death	COVID-19 related deaths with onset at least 28 days after last vaccination	Adults>= 18 years old	Single dose Ad26.COV2.S  Two doses Ad26.COV2.S (maximum of 70 days between doses)  Booster dose Ad26.COV2.S (minimum of 71 days between doses)	LTFU- Outside vaccinations	Number of subjects with events and incidence rates per 100 person-years
Severity of breakthrough infections	The severity of COVID-19 cases may be evaluated by the severity and number of symptoms (severity) of COVID-19 cases, ratio of severe/critical COVID-19 cases (number of severe/critical COVID-19/ total number of moderate and severe/critical COVID-19) and ratio of long COVID-19 cases (duration of more than 28 days) (the number of long moderate/severe COVID-19/ total number of moderate/severe COVID-19)	Adults>= 18 years old	Single dose Ad26.COV2.S  Two doses Ad26.COV2.S (maximum of 70 days between doses)  Booster dose Ad26.COV2.S (minimum of 71 days between doses)	LTFU – Outside vaccinations	Percentage of cases that are severe/critical; Percentage of cases that have a long duration (duration of more than 28 days)
Immunogenicity of Ad26.COV2.S at available timepoints	Analysis of antibodies binding to the SARS-CoV-2 S protein by ELISA	Adults>= 18 years old	Two doses Ad26.COV2.S	LTFU- Outside vaccinations	GMR, responder rate

Objectives	Endpoints/Variable	Population	Intervention	Intercurrent events	Summary measure

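### The long COVID-19 ratio is limited to moderate/severe cases in the Section 1.1 estimand but carries no severity limit in Section 5.2.7, so the two sections give different values for one endpoint

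*SAP*

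**What the plan says.** The estimand table for the open-label active analysis (SAP Section 1.1, row on severity of breakthrough infections) defines the long COVID-19 ratio as "the number of long moderate/severe COVID-19/ total number of moderate/severe COVID-19". The summary-measure column of the same row does not repeat the severity limit. It reads "Percentage of cases that have a long duration (duration of more than 28 days").

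Section 5.2.7, under the Long COVID-19 ratio, gives the calculation: "The long COVID-19 ratio will be calculated as the ratio between long COVID-19 cases and both long and short cases". The split is by duration only: "An episode lasting more than 28 days is considered to be a long COVID-19 case and an episode lasting 28 days or less a short" one. The result is shown for each study dose cohort.

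Just before this, Section 5.2.7 defines the companion measure with its severity classes named: "The severity ratio will be calculated as the ratio between severe cases and both severe and moderate cases".

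**The concern.** One named endpoint has two formulas. Long and short, cut at 28 days, together cover every episode, so the 5.2.7 denominator has no boundary by severity. The estimand's denominator does. A programmer working from 5.2.7 and one working from Section 1.1 would deliver different tables under the same title.

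At stake is what the printed percentage means. Under the estimand it describes how often moderate or severe disease persists beyond 28 days. Under 5.2.7 it mixes that with the share of mild cases and their own persistence, so it could move while persistence of moderate/severe disease stays the same.

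**Working it through.** **Inputs from the SAP**

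- Section 1.1: numerator and denominator limited to moderate/severe.
- Section 5.2.7: no severity limit; cut at 28 days.
- Section 1.1, symptomatic endpoint: "Symptomatic COVID-19 according to mild, moderate or severe programmed algorithmic definition". Mild is therefore a separate class. Section 5.2.4 likewise lists symptomatic COVID-19 apart from moderate to severe/critical COVID-19.

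The SAP states no value for this ratio, so there is no figure to reproduce. It also gives no mild share and no long-duration rate; the values below are assumptions chosen to show the range.

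**Effect of the missing restriction**

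Let *a* be the proportion long among moderate/severe episodes, *b* the proportion long among mild episodes, and *m* the mild share of all cases.

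- Estimand (1.1): *a*
- 5.2.7 as written: (1 − *m*)·*a* + *m*·*b*
- Difference, 5.2.7 minus estimand: *m*·(*b* − *a*)

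With *a* = 20% (assumed), the estimand is 20% throughout and 5.2.7 gives:

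| Mild share *m* | *b* = 0% | *b* = 10% | *b* = 20% | *b* = 30% |
|---|---|---|---|---|
| 5% | 19.0% | 19.5% | 20.0% | 20.5% |
| 10% | 18.0% | 19.0% | 20.0% | 21.0% |
| 30% | 14.0% | 17.0% | 20.0% | 23.0% |

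Example: *m* = 30%, *b* = 0% gives 0.7 × 20% + 0.3 × 0% = 14%; *b* = 30% gives 0.7 × 20% + 0.3 × 30% = 23%. The two formulas agree only if there are no mild cases or if mild episodes are long exactly as often as moderate/severe ones.

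**Episodes whose end is not observed**

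Section 5.1.1.2 stops the efficacy data 30 days before site approval of Protocol Amendment 7 (PA7), and Section 1 says the symptom diary stopped at PA7. For the latest counted onset, duration as last day − first day + 1 can be observed for 30 days (last diary the day before PA7) or 30 + 1 = 31 days (last diary on that day). Both exceed 28, so the switch to passive follow-up cannot by itself turn a long episode into a short one.

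What remains is loss to follow-up, discontinuation, death or a stopped diary within 28 days of onset. The SAP gives no rule for these. With an assumed 20% long among resolved episodes and a share *u* unresolved:

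| *u* | counted short: (1 − *u*) × 20% | left out | counted long: (1 − *u*) × 20% + *u* |
|---|---|---|---|
| 2% | 19.6% | 20% | 21.6% |
| 5% | 19.0% | 20% | 24.0% |
| 10% | 18.0% | 20% | 28.0% |

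The handling choice matters only as far as *u* is material, and the SAP does not show what *u* is.

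**The case against.** The best defence is that 5.2.7 is shorthand. It never says that all cases are included. It only omits a restriction that Section 1.1 spells out, and the two can be read together. This does not remove the conflict. The neighbouring severity ratio does name its classes, so a reader would expect the same here, and the summary-measure column speaks only of cases, so the estimand row does not settle the matter either. Section 5.2.4 refers case classification to the double-blind SAP, which is not at hand, but both formulas in conflict are in this SAP.

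The defence is right about the weight of the point. The ratio is a supportive, untested description, and Sections 5.1 and 5.2 rule out comparisons between groups.

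A reader might infer three stronger things that the document does not support:

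- **That unresolved episodes are counted as short.** Section 5.2.7 classifies by how long an episode lasts and is silent on one with no recorded end. A rule may sit in the double-blind SAP, and the 30-day window already closes the PA7 route to truncation.
- **That the ratio comes out too low.** This needs mild episodes to be long less often than moderate/severe ones, or unresolved episodes to be counted as short. The first is plausible but appears nowhere in the SAP, and the sign reverses if it fails. The second is an unstated rule.
- **That cohorts would be wrongly contrasted because their mild shares differ.** The SAP gives no mild share by cohort or over time, and it bars the contrast.

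**Conclusion.** The inconsistency stands. Followed as written, Section 5.2.7 produces a different quantity from the estimand in Section 1.1 whenever mild cases occur and their long-duration rate differs from that of moderate/severe cases. The size and sign are *m*·(*b* − *a*), and neither can be fixed from the SAP. Under the assumed *a* = 20% and *b* from 0% to 30%, the shift is −2 to +1 percentage points at a 10% mild share and −6 to +3 points at 30%.

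Episodes with no recorded end and at most 28 days of observation are an unspecified edge case. No direction of bias is claimed for them.

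The correction is worth making because a printed endpoint should match its own definition. No test or primary conclusion depends on it.

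**What to change.** In Section 5.2.7, limit both numerator and denominator of the long COVID-19 ratio to molecularly confirmed moderate to severe/critical episodes. Put the same limit into the summary-measure column of the severity row in the Section 1.1 estimand table; editing 5.2.7 alone would leave that column open. The cost is one sentence in each place and one filter in the program. The downside is a smaller denominator and so a less precise percentage per cohort.

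Optionally, report for each cohort the number of episodes with no recorded end and 28 days or less of observation, and state how they are classified. Showing the count beside the ratio is safer than quietly dropping these episodes, because those still symptomatic when lost may differ from the rest and leaving them out could itself be informative.
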